Study Summary

Title:	Contrast-Enhanced Ultrasound for Diagnosis and Therapy of Cholangiocarcinoma
Précis:	20 patients with biopsy-proven intrahepatic cholangiocarcinoma (ICC) or other non-HCC tumors in the liver will receive their standard of care (SoC) sub-lobar transarterial radioembolization (TARE), in addition to four sessions of ultrasound contrast infusion and ultrasound scanning. One session will be within 1 month prior to treatment and the other three will be at different time points after treatment. The treatment outcomes will be compared to a historical group of similar patients receiving TARE alone. The main hypotheses are that contrast-enhanced ultrasound (CEUS) can be used to predict non-HCC response to TARE prior to therapy, improve the sensitivity of these tumors to radiotherapy, and assess treatment response earlier than the current clinical standard.
Objectives:	To evaluate the utility of CEUS-derived quantitative measures in predicting tumor response before and in the early phases after TARE treatment, and to evaluate the safety and efficacy of microbubble cavitation in improving TARE treatment.
	Primary: 
• To determine the ability of quantitative volumetric CEUS to predict tumoral response to TARE prior to therapy.
	Secondary: 
• To characterize the safety and preliminary efficacy of using localized UCA inertial cavitation to improve non-HCC tumor response to radioembolization.• To determine if CEUS estimated tumor perfusion and residual vascularity can predict non-HCC tumor response to radioembolization 7-14 days post treatment.• To evaluate tumoral response using the patient's 1 month MRI (obtained clinically) and determine the accuracy of MR or CT tumor evaluation at this earlier time point.
	Exploratory: 
• To examine the utility of SHAPE to noninvasively monitor tumoral interstitial fluid pressure (IFP) and provide an early biomarker of radiotherapy response.
Population:	20 patients with intrahepatic cholangiocarcinoma (ICC) or other non-HCC tumors receiving sub-lobar transarterial radioembolization

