1.1 Background Information

Intrahepatic non-HCC tumors

A variety of both primary and metastatic cancers present in the liver. Cholangiocarcinoma is an aggressive epithelial tumor arising from the lining of the biliary tract with high morbidity and extremely poor prognosis. There are three tumor subtypes defined by the anatomical region from which they arise – intrahepatic, peri-hilar and distal (extrahepatic) bile ducts. Approximately 10% of cholangiocarcinomas are intrahepatic. Intrahepatic cholangiocarcinoma (ICC) is the second most common primary liver malignancy after hepatocellular carcinoma (HCC), accounting for 10-20% of primary liver tumors¹. Sadly, ICC incidence and mortality have been increasing in Western countries over the past two decades, highlighting the need to improve therapeutic options². Additionally, many non-liver cancers will first metastasize to the liver. These include (but are not limited to) uveal melanoma, neuroendocrine tumors, pancreatic cancers, breast cancer, and colorectal cancers. Management options for non-HCC tumors in the liver are limited and the disease generally portends a poor prognosis. Liver transplant is currently not an option and while curative surgical resection is the first line of therapy in patients with ICC without extension beyond the regional lymph nodes, it is only possible in less than 30% of cases with median disease free survival of 26 months^{1,3}. The majority of patients present with locally advanced or metastatic disease and are treated with systemic chemotherapy or loco-regional therapies. Liver-directed therapies including thermal ablation, transarterial chemoembolization (TACE), and transarterial radioembolization (TARE) are indicated for localized tumors^{4,5}.

Transarterial radioembolization

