4.1 Eligibility Criteria

4.1.1 Inclusion Criteria

The patients enrolled in this project will be adults over the age of 18 capable of providing written informed consent. Based on the study protocol and Optison contraindications, inclusion criteria for this trial are as follows:

- Be scheduled for sub-lobar radioembolization therapy of a previously untreated non-HCC tumor greater than 1 cm but small enough to be fully visualized in the ultrasound 3D volume (approximately 6 cm maximum diameter, but depth dependent)
- Be at least 18 years of age.
- Be medically stable.
- If a female of child-bearing age, have a negative pregnancy test prior to each ultrasound exam.
- Have signed Informed Consent to participate in the study.

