Post treatment ultrasound exams will take place 2-4 hours post radioembolization in Interventional Radiology's recovery unit prior to single photon emission computed tomography (SPECT) imaging, and again 7 and 14 days post treatment in Thomas Jefferson University's Interventional Radiology Division. Both of these locations have full time nursing support and with patient physiological monitoring. Specific imaging time points are based on times when patients are present or returning to the hospital for regular follow up, experiences with our study enrollment in ongoing HCC trials, and at a time when the Y90 spheres are still active. All contrast injections will be supervised by a board certified physician (Drs. [name], [name], [name], or [name]) with resuscitation equipment in immediate proximity during CEUS exam. Patient vital signs will be monitored and recorded throughout the visit. Tumor characteristics (size and location) will also be recorded for subset analysis to study how these factors influence treatment.

Similar to the pre-treatment exam, B-mode and Doppler volumes will be acquired for each exam post-TARE. Following these acquisitions, 5 milliliters of activated Optison will be suspended in 50 ml of saline and infused through an 18- to 22-gauge angiocatheter placed in a peripheral arm vein at a rate of 120 ml/hour. This total Optison administration falls within the product insert dosage guidelines (up to 5 ml within a 10 minute period and up to 8.7 ml in any one study). Following peak enhancement, a destructive (high MI) pulse will be generated across the selected volume. This will be performed using a modified software platform (created as part of R01 CA199646) that can be customized for transmission of UTMD flash replenishment sequences across a volume. The system will be set a center frequency of 2.1 MHz, with pulse lengths of 20 μ s and a line density of 4. Acoustic pressure amplitudes will be adjusted as necessary to ensure inertial microbubble cavitation. Importantly, this research software system provides range gated

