11.2 Analysis Plans

In general, categorical data will be summarized as counts and percentages (or proportions) and continuous data will be summarized with descriptive statistics such as mean, standard deviation (SD), median, and range. All statistical analysis will be performed by [name] using SAS version 9.4 (Cary, NC). All statistical tests will be conducted at a nominal $\alpha=0.05$ level. For H1 (see Section 11.1 above), the respective relationships between the CEUS-derived contrast reperfusion time, degree of tumor enhancement relative to the surrounding parenchyma, tumoral IFP and 3D morphological features of the vasculature with the patients' subsequent mRECIST diagnosis (3 levels: stable disease, partial response, or complete response) will be evaluated by testing for mean difference in the CEUS measures between response levels by analysis of variance (ANOVA). Historical controls ($n=20$) will be identified from a pool of recently treated non-HCC patients at Jefferson that meet study eligibility criteria for the study and match our enrollees by propensity score based on a logistic regression model including patient age, tumor size, bilirubin and ECOG performance score and utilizing a greedy matching algorithm. Testing for the effect of radioembolization on tumor response in H2 will be conducted using non-parametric Mann-Whitney U-tests of the differences in mRECIST distributions between historical controls and enrolled patients. The difference in time-to-event endpoints (i.e., to next treatment or death, respectively) between the treated and historical control patients for H3 will be estimated and tested using Kaplan-Meier survival methods and log-rank tests. Differences in safety data will be evaluated for H4 with descriptive statistics, but not statistical hypothesis tests. A similar ANOVA approach taken for evaluating H1 will be taken for evaluating the means of CEUS measures at different times (2-4 hours, 1 week, and 2 week, respectively) of tumor perfusion and residual vascularity values between response levels to address H5 and SHAPE IFP values for addressing H8, as well as the means of changes from baseline in these measure for addressing H6 and H9. The agreement on response between mRECIST response diagnoses at 1 month and 3-6 months post-TARE will be tested using McNemar's test.

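### The propensity score that selects historical controls leaves out tumor type, so a systematic difference in tumor mix would confound the secondary comparisons H2 and H3

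*Combined protocol and SAP*

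**What the plan says.** Section 11.2 takes controls (n=20) from "a pool of recently treated non-HCC patients at Jefferson that meet study eligibility criteria for the study" and matches them to the enrolled patients on a propensity score from a "logistic regression model including patient age, tumor size, bilirubin and ECOG performance score and utilizing a greedy matching algorithm". H2 compares mRECIST distributions between the groups with a Mann-Whitney test. H3 compares time to next treatment and overall survival with Kaplan-Meier methods and log-rank tests. Neither test is adjusted or stratified.

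Eligibility is wide with respect to tumor type. The Study Summary admits "biopsy-proven intrahepatic cholangiocarcinoma (ICC) or other non-HCC tumors in the liver". Section 4.1.1 requires only "sub-lobar radioembolization therapy of a previously untreated non-HCC tumor greater than 1 cm", up to a size that fits the ultrasound volume. Section 1.1 gives examples of cancers that spread to the liver: "uveal melanoma, neuroendocrine tumors, pancreatic cancers, breast cancer, and colorectal cancers".

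Section 5.8 is the only place that plans an analysis by tumor characteristics, and it names two: "Tumor characteristics (size and location) will also be recorded for subset analysis to study how these factors influence treatment".

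**The concern.** The trial is not randomized and has no concurrent control, so the matching is the only protection against case-mix differences. It balances, at best, the four variables in the model. Shared eligibility does not balance tumor type, because eligibility does not restrict it. The blinded mRECIST reads in section 11.3.2 guard against reader bias, not against a different mix of diseases.

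Two conditions are needed for harm: outcome after TARE must differ by tumor type, and enrolled patients must differ systematically from controls in their mix. If both hold, the difference passes straight into H2 and H3, and into the descriptive safety comparison H4. It could be credited to cavitation or could mask a real effect. This matters because the historical comparison is the only efficacy evidence for the cavitation objective in section 2.1.2. H1 is analyzed within the enrolled patients and is untouched.

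**Working it through.** **The plan's own figure.** Section 11.4 states 80% power at 0.66 SD with 20 per arm. A paired t-test on 20 pairs, two-sided 5%, gives 79.9%, so the figure reproduces on that reading. It says nothing about tumor mix, and the documents contain no figure that does.

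**Inputs for an illustration**
- 20 per group; nominal 5% level (sections 11.2 and 11.4), taken as two-sided.
- Three outcome levels: no response, PR, CR. Responders are split 2:1 PR to CR, following the 50% and 25% expected in section 11.4.
- Two tumor classes. Response by class is an assumption: 60% versus 25% as a wide contrast, 50% versus 35% as a mild one. The values 25% and 60% are the ends of the overall response range in section 1.1; the protocol does not attribute that range to tumor type.
- The share of the better-responding class in each group is also an assumption.
- No true effect of cavitation.

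**Spurious shift in response** = (share in enrolled − share in controls) × (response difference between classes)
- 70% vs 40%, wide contrast: 0.3 × 0.35 = 10.5 points
- 80% vs 20%, wide contrast: 0.6 × 0.35 = 21 points
- 70% vs 40%, mild contrast: 0.3 × 0.15 = 4.5 points
- 80% vs 20%, mild contrast: 0.6 × 0.15 = 9 points

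**False-positive rate of the planned H2 test.** Simulation with a tie-corrected, two-sided Mann-Whitney test without continuity correction (200,000 runs; 100,000 for the 60/50 and 60/40 rows):

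| Better class, enrolled / control | 60% vs 25% | 50% vs 35% |
|---|---|---|
| Same underlying mix | 4.9% | 5.1% |
| 60 / 50 | 5.4% | 5.0% |
| 60 / 40 | 7.2% | 5.3% |
| 70 / 40 | 9.7% | 5.9% |
| 80 / 20 | 25.4% | 8.5% |

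The first row lets the realized mix vary by chance and the rate stays near 5%. Only a systematic difference does damage.

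**The reverse direction.** With a true gain of 25 points in each class, the wide contrast, and a mix of 40% enrolled versus 70% control, the planned test has 13.5% power. A van Elteren test stratified by class has 28.3%.

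**The proposed analysis.** The van Elteren test holds 4.7% to 5.0% in the same-mix, 70/40 and 80/20 cases under both contrasts. With class matched exactly (10 and 10 in each group) and a true gain of 25 points, power is 0.30 for Mann-Whitney and 0.33 for van Elteren under the wide contrast, and 0.32 for both under the mild one.

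**H3** was not quantified. The only type-specific survival figure in the documents is the 15.5-month median for ICC in section 1.1, and it has no comparator.

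**The case against.** The strongest case against the point concerns its weight.

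- **Both conditions are assumed.** The documents give no response or survival by tumor type and no expected mix. Controls come from the same institution, were recently treated and meet the same criteria, which limits drift. This stands, and it is why the size is given only as a range. Section 1.1 does say that TARE is increasingly used for metastases, so drift in mix is possible.
- **The 25% is an extreme case.** It needs the widest contrast together with an 80/20 mix. For 60/40 or milder, inflation is about 2 points at most. This stands, and the table shows it.
- **Exact matching might suffice without stratified tests.** With class matched 10 and 10, the ordinary Mann-Whitney test has a false-positive rate of 3.6% (wide contrast) or 4.6% (mild), so it no longer produces excess false positives. But it is then conservative. Stratifying brings the rate back to nominal and loses no power, so it is worth having, though it is the lesser half of the fix.
- **Two classes may be too coarse.** Suppose 8 ICC patients per group respond at 40%, and 12 metastases per group are a mixture responding at 60% or 25%, split 9/3 versus 4/8. The stratified test then gives 7.4%; with 10/2 versus 2/10 it gives 13.3%. In both cases this is no better than the unstratified test. This stands: the near-5% result for van Elteren holds only if the classes capture the outcome difference.
- **It is a pilot.** Efficacy is called preliminary, section 11.4 expects larger randomized trials, and section 11.3.2 expects time to next treatment and survival to outlast the study. This lowers the stakes but does not remove them, since a distorted H2 would misinform the decision on a larger trial.

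**Conclusion.** The concern holds. The matching model omits tumor type, eligibility admits many tumor types, and nothing elsewhere in the protocol compensates. Followed as written, the plan leaves H2 and H3 open to confounding by tumor mix, and H4 is exposed in the same way descriptively.

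Under the assumptions shown, the H2 false-positive rate runs from about 5% (same mix, or mild contrast with mild imbalance) through about 10% (70/40, wide contrast) to about 25% (80/20, wide contrast). The direction of any bias is unknown. H3 is exposed by the same reasoning, but its size cannot be derived from the documents. The primary analysis is not affected. This is a gap in a secondary comparison that should be closed because closing it is cheap, not a flaw that undermines the trial. Confidence is medium, because both the contrast between tumor types and the imbalance are assumed.

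**What to change.** In section 11.2:
1. Define a collapsed tumor-type class before controls are selected: at least ICC versus metastasis, finer by primary site only where the historical pool allows.
2. Match exactly on that class, then match within class on the existing propensity score.
3. Report the tumor-type mix of both groups, by primary site where known, so that residual differences within metastases can be seen.
4. Stratify the H2 and H3 tests by the collapsed class only: van Elteren test and stratified log-rank test.

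The cost is a change of SAP wording and one more chart-review field for controls. The sample size does not change, and in the simulation stratifying H2 by two classes costs no appreciable power.

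The downsides are fewer candidate controls per class, hence possibly looser matches on age, size, bilirubin and ECOG, and possible residual differences by primary site. Strata by individual primary site would be too sparse at 20 per group. Section 6.1 puts eligible patients at about 50–60 per year, so two classes may be workable. However, the size and mix of the historical pool are not stated, and biopsy is not among the inclusion criteria in section 4.1.1. The sponsor should therefore confirm that tumor type is documented for candidate controls, and which classes are feasible, before fixing the definition.

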11.4 Sample Size Considerations

Sample size for this pilot study is primarily driven by patient availability and larger, multi-center randomized trials will likely be needed to fully demonstrate efficacy. However, for the primary objective, a sample size of 20 patients (of which we expect 25% having stable disease, 50% partial responders, and 25% complete responders) will provide 80% power to detect a 0.76 standard deviation difference in CEUS measurement means (e.g., mean contrast perfusion time) between mRECIST response levels, by analysis of variance (ANOVA) with a nominal 5% type I error rate. Similarly, in analyses comparing the prospective treated patients to matched historical control patients, 20 patients per arm will provide 80% power to detect a relative effect size of 0.66 standard deviations by t-test with a nominal 5% type I error rate (i.e., a moderately large, but reasonable effect given our current data in HCC patients).

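### H2 and H3 test propensity-matched controls as unadjusted independent samples: mostly conservative, at some cost in power, and the stated 80% power fits only a paired test

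*Combined protocol and SAP*

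**What the plan says.** Section 11.2 (Analysis Plans) describes both the selection of controls and the tests.

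- **Source of controls.** The 20 controls "will be identified from a pool of recently treated non-HCC patients at Jefferson".
- **Matching.** They must meet eligibility and "match our enrollees by propensity score based on a logistic regression model including patient age, tumor size, bilirubin and ECOG performance score", "utilizing a greedy matching algorithm". No caliper, pool size or balance check is stated. Twenty controls for 20 enrollees implies 1:1.
- **H2 (tumor response).** Testing "will be conducted using non-parametric Mann-Whitney U-tests of the differences in mRECIST distributions between historical controls and enrolled patients".
- **H3 (time to next treatment, overall survival).** Differences "will be estimated and tested using Kaplan-Meier survival methods and log-rank tests".
- **H4 (safety).** Descriptive only, so not affected.

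Section 11.4 (Sample Size Considerations), referring to matched historical controls, says that "20 patients per arm will provide 80% power to detect a relative effect size of 0.66 standard deviations by t-test" at a nominal 5% type I error rate. It does not say whether the t-test is paired, or one- or two-sided.

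No other section gives a paired, pair-stratified, cluster-robust or covariate-adjusted analysis for H2 or H3.

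**The concern.** Matching on prognostic covariates makes the two groups more alike than two independent samples would be. A test that ignores this still counts the covariates' contribution to the outcome as noise. Its standard error is then too large, it rejects less than 5% of the time under no effect, and it misses real effects that an adjusted test on the same 40 patients could detect. If matching is poor, the remaining imbalance goes uncorrected and the error can run the other way.

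H2 carries the plan's only test of preliminary efficacy on tumor response. With 20 enrollees and no replacement of withdrawals, precision lost in the analysis cannot be bought back. The sample size statement also appears to rest on a different analysis from the one specified, so the plan's stated sensitivity for this comparison is in doubt.

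**Working it through.** **1. The plan's own figure.** Inputs from Section 11.4: n = 20 per arm, d = 0.66, alpha = 0.05, power 80%.

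- Two independent samples, two-sided: noncentrality d√(n/2) = 0.66 × √10 = 2.087 on 38 df. Power is 53.0%, and the effect detectable with 80% power is 0.91 SD. One-sided, these become 65.7% and 0.80 SD. Neither matches the plan.
- Paired, 20 pairs, two-sided: noncentrality d√n = 0.66 × √20 = 2.952 on 19 df. Power is 79.9%, and the detectable effect is 0.660. This matches.
- An independent two-sample t-test needs 37 to 38 per arm for 80% power at 0.66 SD.

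**2. Units of the paired figure.** The 0.66 is in SDs of the within-pair difference, which equal √(2(1−ρ)) outcome SDs, where ρ is the within-pair correlation. In outcome SDs the paired detectable effect is 0.660 × √(2(1−ρ)): 0.93 at ρ = 0, 0.84 at 0.2, 0.78 at 0.3 and 0.66 at 0.5. So 0.66 outcome SDs needs ρ = 0.5.

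**3. Effect of ignoring the pairing.** The variance of the mean difference is 2σ²(1−ρ)/n, but an independent-samples test uses 2σ²/n. The large-sample size is therefore 2[1 − Φ(1.96/√(1−ρ))]. The documents do not give ρ, so it is varied. The simulated columns use a latent normal outcome cut at the 25/50/25 split of Section 11.4 (20,000 runs; 5,000 for log-rank, about 70% events).

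| ρ | Formula size | Mann-Whitney size | Log-rank size | Power at 0.66 SD: Mann-Whitney / signed-rank |
|---|---|---|---|---|
| 0 | 5.0% | 5.2% | 5.8% | 44.7% / 41.8% |
| 0.1 | 3.9% | 4.1% | 4.1% | 43.4% / 44.3% |
| 0.2 | 2.8% | 3.1% | 3.5% | 43.3% / 47.5% |
| 0.3 | 1.9% | 2.6% | 2.9% | 43.6% / 51.5% |
| 0.5 | 0.6% | 1.2% | 1.1% | 43.0% / 61.2% |

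**4. What greedy matching delivers.** With four normal covariates, no caliper, pools of 40 or 100 and covariates explaining 10 to 50% of outcome variance, the within-pair correlation was only 0.02 to 0.33. Pairing alone is not a safe repair: with a pool of 40, groups 0.4 SD apart and strong covariates, Mann-Whitney rejected 5.4 to 6.0% under no effect, but a paired t-test rejected 8.0 to 11.4%.

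**5. Planned test against covariate adjustment.** Same matching, three response levels at 25/50/25. Pool size, baseline gap and explained variance (R²) are all assumed.

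- Mann-Whitney null rejection: about 2.4 to 5.3% in every setting except a pool of 40 with groups 0.5 SD apart on each covariate, where it was 5.8 to 8.3%. Other simulation sets put that corner at up to 10.5%.
- Rank ANCOVA on the four covariates: 4.0 to 6.0% throughout; up to 7.1% in one other set.
- Power gain of rank ANCOVA with groups similar at baseline: about 2 to 4 points at R² = 0.1, rising to 12 to 15 at R² = 0.4.
- Proportional-odds model, n = 40: the likelihood-ratio test rejected 6.3 to 10.1% under no effect across 27 settings and the Wald test 5.0 to 8.8%. A further check of the model gave 5.1 to 6.6%.

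**6. Likely pool size.** Section 6.1 gives about 50 to 60 eligible patients a year, so 40 is 40/60 to 40/50, or 0.67 to 0.8 of a year. Two years would give 100 to 120, if past volume was similar. With a pool of 110, Mann-Whitney rejected 2.5 to 4.5% even with groups 0.5 SD apart, and log-rank 3.9 to 5.2%. Log-rank reached 8.8 to 9.3% only in the small-pool corner with strong covariates.

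**The case against.** The case for leaving the plan alone is fair in several respects. Whether propensity-matched samples need a paired analysis is debated. The planned test is usually conservative, so it seldom creates a false claim. The power gain depends on an explained variance that appears nowhere in the documents, and Section 4.1 narrows the covariates: bilirubin above 2 mg/dL is excluded, tumors run from 1 to about 6 cm, and patients must be medically stable. At 5 to 10% explained variance, one set of runs found almost nothing to gain (48.9% adjusted against 49.2%, and 51.4% against 48.9%). H2 and H3 are secondary, Section 11.4 defers efficacy to larger randomized trials, and Section 11.3.2 expects the time-to-event outcomes to outlast the study. Adjusted models can also misbehave with 40 patients, as the proportional-odds results show.

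Most of this limits the size of the point and the choice of remedy. It does not explain why covariates judged important enough to match on are then left out of the tests. Nor does it reconcile Section 11.4 with Section 11.2. Covariate adjustment also avoids the paired-or-unpaired debate, because it does not depend on pairing.

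A reader might infer that the plan inflates false positives. The documents do not support that. Inflation needed a small pool together with a sizeable gap on every covariate; the documents state neither, and Section 6.1 points to a larger pool if more than one year of patients is used. The word used there for how recently controls were treated is not defined, so the small-pool case cannot be ruled out.

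**Conclusion.** The mismatch is in the text and nothing elsewhere repairs it. For H2 the main consequence is a conservative test and some lost power, of the size shown in step 5 above. That rests on assumed explained variance, a normal latent outcome, equally prognostic covariates and 1:1 matching without a caliper. Log-rank for H3 behaves in the same direction, but no adjusted survival analysis was simulated, so the H3 recommendation is supportive only.

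The power statement is a firmer finding because it needs no such assumptions: "by t-test with a nominal 5% type I error rate" gives 80% at 0.66 SD only if the test is paired, which Section 11.2 does not plan. A reader might take the gap, 79.9 − 53.0 = 26.9 points, as the price of dropping the pairs. It is not, because the two figures measure 0.66 in different units unless ρ = 0.5, and matching on these covariates gave 0.33 at most.

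The change is worth making before controls are selected. Its priority is modest, given secondary aims in a pilot.

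**What to change.** - **H2, Section 11.2.** Make the main test a rank ANCOVA of mRECIST level on group with age, tumor size, bilirubin and ECOG score as covariates. Keep Mann-Whitney as a sensitivity analysis. Do not substitute an uncorrected proportional-odds likelihood-ratio test at n = 40.
- **Matching.** Report standardized differences for the four covariates after matching.
- **H3.** Beside Kaplan-Meier and log-rank, add as supportive a Cox model with the logit of the propensity score as its single covariate and variance clustered on the matched pair.
- **Section 11.4.** Restate the power to fit the chosen analysis. If independent tests are kept, the detectable effect on the t-test basis is about 0.91 SD.

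The cost is SAP wording, since the covariates are already needed for matching. The downsides are four degrees of freedom, reliance on a model, and sometimes lower power than Mann-Whitney when the groups differ at baseline, mostly where that imbalance biases Mann-Whitney. Adjustment does not remove unmeasured or calendar-time differences from historical controls.
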